Power calculations were conducted based on an intended sample size of 504 and assumed two-sided tests with a 0.05 type I error rate. Power calculations were focused on reduction of STI incidence as it was the more conservative analysis. A 25% attrition rate, assumed to be high and to be expected for this population, resulted in an assumed $n=378$ participants at follow-up. Power calculations were based on a two-sided Poisson regression of a dependent variable of counts (i.e. number of incident STI cases) on a binary independent variable (treatment group) with proportion of 0.50 (i.e. 189 participants) in each group adjusting for age, marital status, employment and homelessness (assuming the estimated R-squared of the independent variable regressed on these four covariates is 0.04). The estimates used for these power calculations were based on a recent HIV intervention study with young Black heterosexual men recruited from STI clinics. The STI clinic study found that comparison group participants were almost 3 times as likely to be STI-infected at follow-up relative to intervention participants. MEN Count pilot data were too small to see intervention impact on STI but did document a baseline STI rate of 13% in this target population. Using these data, the proposed sample size of $n=378$ would have at least 80% power to detect a rate ratio (Group 1/Group 2) of at least 0.28 (intervention incidence rate=2%), 0.31 (intervention incidence rate=2.5%), 0.34 (intervention incidence rate=3%) or 0.36 (intervention incidence rate=3.6%), respectively, assuming the 1-year cumulative STI incidence rate in the Comparison Group is 7%, 8%, 9%, or 10%.

Though difference-in-difference multivariate regression models were used to assess outcomes (see below), analyses were also performed as outlined by power calculation assumptions (e.g. utilizing Poisson models and specified covariates) and also found null results for the incident STI outcome.

Analytic Plan

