Outcome analyses were designed to focus on four outcomes of interest (defined in greater detail below): incident non-viral STI, sexual risk, homelessness, and unemployment. The primary comparison of outcomes by treatment group was assessed using mixed-effects multivariate regression models (logistic and multinomial, dependent on outcome) with random effects on individual to account for repeated measurements over time. The treatment effect was evaluated via a time-by-treatment arm interaction term. A categorical time effect was used. This treatment effect can be interpreted as the individual-level effect of the intervention, and this analytic strategy addresses problems of attrition, missing data, variable timing of subject visits and other possible unintended violations of design common to longitudinal studies. Demographic covariates were included in all outcome models if they were significantly associated with treatment group at baseline in bivariate chi-squared tests at $p<0.20$. For each outcome, additional potential covariates were included if they were associated with the given outcome in bivariate chi-squared tests at $p<0.05$. Dose effects of the MEN Count intervention were evaluated using a similar analytic strategy, examining a time-by-dose interaction instead of time-by-study arm.

Outcome Definitions

Pursuant to previous HIV prevention research with Black heterosexual men that used ordinal index of sexual risk categorization, sexual risk was categorized as very low, low, medium, and high.² Very low sexual risk was defined as having one partner and consistent condom use. Low sexual risk was defined as having multiple partners and consistent condom use OR one partner and no/inconsistent condom use. Medium sexual risk was defined as having multiple partners, no/inconsistent condom use and not participating in transactional sex. High risk was defined as having multiple partners, no/inconsistent condom use, and participating in transactional sex. Participants reporting sex with men in the prior 90 days (n=20) or who reported that they themselves or (one of) their partner(s) was HIV-positive (n=31) were excluded from the sexual risk outcome analysis given the known differential HIV risk profile for these subpopulations and small numbers of participants in each.

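### For incident STI, the plan says its model addresses variable visit timing, but the time term described is categorical and no person-time term is described

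*Combined protocol and SAP*

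**What the plan says.** The Background section sets assessments, with HIV/STI testing, at baseline, 6 months and 12 months. No visit windows are given.

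The Analytic Plan makes a mixed-effects regression the primary comparison for all four outcomes, with a random effect on the individual and a time-by-arm interaction. It states: "A categorical time effect was used". It then says that "this analytic strategy addresses problems of attrition, missing data, variable timing of subject visits" and other departures common in longitudinal studies.

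The Power Calculation section rests on a "two-sided Poisson regression of a dependent variable of counts (i.e. number of incident STI cases) on a binary independent variable (treatment group"), adjusted for age, marital status, employment and homelessness. The effect is a rate ratio, and the comparison-group inputs are 1-year cumulative incidences of 7% to 10%. No offset, exposure or person-time term is mentioned. The section closes by saying that STI was also analysed along the lines of these assumptions, and that this too gave a null result.

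The Analytic Plan promises fuller definitions of all four outcomes, but the Outcome Definitions section covers only sexual risk, homelessness and employment. The interval over which an STI counts as incident is not defined.

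**The concern.** A test for incident STI picks up infection acquired since the previous test, so the chance of a positive grows with the interval. A categorical time term gives every man in a category the same time value. On the natural reading the categories are the nominal visits, so a 6-month test taken at month 5 and one taken at month 9 are treated alike. So are two 12-month tests, one following a 6-month test and one following a missed visit. A random effect on the individual models correlation between a man's own records; it does not adjust for how long he was at risk.

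In a count model without person-time, a man last tested at 6 months counts like a man followed for 12.

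At stake is the comparability of the arms on STI. Balance in timing cannot be taken for granted: the Background calls the design quasi-experimental (the Pilot Testing text refers to an RCT), 25% attrition was expected, and the Process Evaluation section mentions follow-up challenges. The time-by-dose analysis is more exposed, because session attendance is not assigned and may go with returning on time.

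**Working it through.** **1. The plan's own figure.** Inputs, all from the Power Calculation section: "assumed two-sided tests with a 0.05 type I error rate"; 504 × 0.75 = 378 men; "with proportion of 0.50 (i.e. 189 participants) in each group"; covariate R² = 0.04; comparison incidence r₀ = 7%, 8%, 9%, 10%; rate ratios 0.28, 0.31, 0.34, 0.36. The Signorini formula for Poisson regression is

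z = [√(N(1−R²)·T·r₀·B²) − 1.96·√V₀] / √V₁,

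with B = ln(RR), V₀ = 1/(0.5 × 0.5) = 4, V₁ = 2 + 2/RR, and exposure T = 1 year for everyone. For the first scenario: √(378 × 0.96 × 0.07 × 1.273²) = 6.416; (6.416 − 3.920)/√9.143 = 0.825; power 79.5%.

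| Comparison incidence | Stated RR | Power | RR at 80% power |
|---|---|---|---|
| 7% | 0.28 | 79.5% | 0.277 |
| 8% | 0.31 | 79.5% | 0.306 |
| 9% | 0.34 | 78.8% | 0.332 |
| 10% | 0.36 | 79.2% | 0.355 |

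The stated 80% is reproduced to within 2 points. The calculation gives every man the same one year at risk.

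**2. Risk by test interval.** Assume 9% one-year incidence (inside the plan's 7–10%), a constant rate, and infections that persist to the test. Monthly rate = −ln(1 − 0.09)/12 = 0.00786; risk over m months = 1 − exp(−0.00786·m).

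| Months since previous test | 5 | 6 | 9 | 12 |
|---|---|---|---|---|
| Chance of a positive | 3.9% | 4.6% | 6.8% | 9.0% |

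These belong under two labels. Under 6 months, tests at months 5 and 9 differ by 6.83/3.85 = 1.77 times. Under 12 months, a man who missed the 6-month test has 9.00/4.61 = 1.95 times the risk of a man who attended it. These are individual risks, not effects on the arm contrast.

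**3. Arm contrast in the Poisson model without an offset, no true effect.** Let p₁ and p₀ be the shares of intervention and comparison men whose only follow-up test is at 6 months, the rest being followed for 12. Mean time at risk is 1 − p/2 years, so the apparent rate ratio is (1 − p₁/2)/(1 − p₀/2).

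- 30% versus 20%: 0.85/0.90 = 0.94.
- 35% versus 15%: 0.825/0.925 = 0.89.
- With the arms exchanged: 0.90/0.85 = 1.06 and 0.925/0.825 = 1.12.

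With a log person-time offset all four return to 1.00. The shares are assumed.

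**4. Effect on error rates.** Simulated two-sided type I error without an offset, 189 per arm:

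| Time at risk, intervention/comparison | 7% per year | 10% per year |
|---|---|---|
| 1.0 | 4.4% | 4.7% |
| 0.9 | 5.2% | 5.7% |
| 0.8 | 7.5% | 9.2% |

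**5. Equal variation in both arms.** With visit-time standard deviations of 0 to 3 months, the same in each arm, a true rate ratio of 0.34 was estimated at 0.337 to 0.341 without an offset. Variable timing alone does not bias the contrast.

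**The case against.** Several counter-arguments carry weight.

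- **The missing offset is inferred from silence.** The sentence on the Poisson analysis lists its features as examples, and a rate ratio can imply person-time. A reader might infer that the model was run without an offset. The documents show only that none is described. The match in step 1 does not settle it, since power is often computed with fixed exposure whatever the final model. Nor is it said outright that the time categories are the nominal visits.
- **The Poisson analysis set is not stated.** The calculation uses 378 men after attrition and one-year incidence. If only men tested at 12 months were analysed, the step 3 scenarios would largely not arise, though late tests would remain.
- **No arm difference is shown.** The comparison programme had the same 60–90 day, three-session structure, and follow-up payments are not split by arm. This does not prove balance, but nothing in the documents demonstrates imbalance.
- **The figures are modest and cover only the supplementary model.** Ratios of 0.94 and 0.89 are small beside the targeted 0.28 to 0.36, and the effect on the primary mixed model's interaction has not been quantified.

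These points limit the size of the problem. They do not rescue the visit-timing sentence for STI, because neither a time category nor a random effect adjusts for interval length.

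**Conclusion.** The point holds for incident STI only. The claim to address variable visit timing is not supported by the models described, and the STI at-risk interval is undefined. Bias in the arm contrast requires timing or loss to differ by arm. Under the assumed scenarios the Poisson rate ratio moves to 0.94 or 0.89 with no true effect, or to 1.06 or 1.12 if the imbalance runs the other way. These figures assume constant incidence and infections that persist to the test; actual size and direction are unknown.

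Three stronger readings are not supported. A reader might infer that the null STI result is an artefact: masking is possible, but no evidence of differential timing is given. A reader might infer that the power statement is wrong: it reproduces. A reader might extend the point to the other outcomes: sexual risk and homelessness use a 90-day recall and employment is current status, so the time between visits does not change their measurement window.

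**What to change.** For incident STI:

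1. Define the at-risk interval, including how a missed 6-month test is handled.
2. In the Poisson model, add log(time from baseline test to last STI test) as an offset, or state that this was done.
3. As a sensitivity analysis to the primary STI model, fit follow-up records only, with a complementary log-log link, a visit-period term and log(time since previous test) as an offset. At a constant rate λ over interval t, log(−log(1 − p)) = log λ + log t, so the offset enters exactly. Baseline records are left out because they have no previous study test, so this offset cannot simply be added to the difference-in-difference model.
4. Report the distribution of test intervals by arm.
5. If this is not done, withdraw the visit-timing claim for STI.

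The cost is one or two derived variables and a short reanalysis, with no new participant contact. The Methods for Data Collection section describes monthly transfer of results from the clinic but does not say that test dates came with them, so their availability must be confirmed. The offset also brings the assumptions of roughly constant incidence and infections persisting to the test, which should be stated. No change is needed for the other three outcomes.

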APPENDIX 1 – MEN Count Study Protocol

Background

The Making Employment Needs (MEN) Count intervention was originally developed and pilot tested using a community-based participatory research approach via funding from the National Institute of Mental Health Grant R21MH085614 grant in Boston, MA.¹ The MEN Count study aimed to determine the efficacy of the MEN Count intervention in terms of its impact on incident STI and heterosexual risk for HIV (i.e., unprotected sex with multiple female sex partners in the past 90 days) among Black heterosexual men (n=454). The two armed quasi-experimental evaluation study enrolled participants in either the MEN Count counseling intervention or an attention comparison group focused on stress reduction. Participants were assessed via survey and HIV/STI testing at baseline and 6- and 12-month follow-ups to test the hypotheses that MEN Count participants, relative to attention comparison participants, would: (a) report a reduction in sexual risk, as measured by unprotected sex episodes and transactional sex in the past 90 days at each follow-up; and (b) have lower incident STI across the follow-up period. This study also aimed to examine the MEN Count intervention's impact on social determinants of health outcomes including employment and homelessness, as well as the intervention's impact on expected mediators (i.e. masculinity ideologies, social-structural factors, and social-cognitive factors) of behavior change, and to explore whether these factors mediated the relationship between the intervention and study outcomes.

Methods/Design

Setting

This study primarily took place in a local STI clinic in Washington D.C.

Curriculum Development

After pilot testing, prompts were embedded into the curriculum to identify checkpoints when MEN Count case managers (CMs) should provide referrals for HIV/STI testing. Prompts were also added to help CMs inquire about the participant's employment situation, potential violence in relationships, HIV/STI testing history and managing HIV risk.

MEN Count Peer Counselors

MEN Count CMs received professional development and training opportunities related to: stress management, anger management, DC resource referrals, mental health status assessment, substance abuse or addiction detection, sensitivity training about gender and sexual identity and LGBT diversity, healthy masculinity, and case note writing.

Pilot Testing

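### The mixed model handles attrition only under a missing-at-random assumption that the plan neither states nor tests, and modest outcome-dependent loss could remove or mask an effect

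*Combined protocol and SAP*

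**What the plan says.** The Analytic Plan section of the combined protocol and SAP names four outcomes: incident non-viral STI, sexual risk, homelessness and unemployment. The main analysis is a mixed-effects regression with a random effect per man, categorical time and an arm-by-time interaction. The section then asserts that "this analytic strategy addresses problems of attrition, missing data, variable timing of subject visits and other possible unintended violations of design". It states no assumption about why data are missing. Nothing in the document plans a comparison of lost and retained men, a report of loss by arm, or a sensitivity analysis for loss that depends on the outcome.

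The Power Calculation section anticipates substantial loss: "A 25% attrition rate, assumed to be high and to be expected for this population". It also describes a supporting Poisson analysis of incident STI, adjusted for age, marital status, homelessness and employment, and reports that this too gave a null result.

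Covariates enter the main models by p-value screening: demographic variables at p<0.20 against arm, others at p<0.05 against the outcome.

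**The concern.** A mixed model fitted by likelihood does not remove the effect of attrition. It in effect predicts a lost man's missing outcomes from his arm, the visit, his covariates and whatever outcomes he did provide. That is valid if, given those data, being lost carries no further information about the outcome that was not seen. The plan claims the benefit without this condition.

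The condition is doubtful in this trial. Every man entered because he was recently homeless or currently unemployed (Eligibility). The outcomes concern the past 90 days or current status (Outcome Definitions), so the relevant state is unseen once contact is lost. A man who has just lost his housing or a job may be harder to find for that very reason. This is an inference; the documents do not report why men were lost. A man lost before six months contributes only baseline data, which may say little about his later state.

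P-value screening adds to the problem. A baseline variable that predicts loss can fail the screen and be dropped, which makes missing at random harder to defend.

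If loss depends on the outcome differently in the two arms, the arm contrast is biased. The STI comparison is exposed because few events are expected. The homelessness, unemployment and sexual-risk models rest on the same claim.

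**Working it through.** **Inputs (all from Power Calculation).** The test is two-sided at 0.05. "Power calculations were conducted based on an intended sample size of 504". Loss is 25%, which "resulted in an assumed $n=378$ participants at follow-up", "with proportion of 0.50 (i.e. 189 participants) in each group". Comparison incidence is 7% to 10% over one year and intervention incidence 2% to 3.6%. The "R-squared of the independent variable regressed on these four covariates is 0.04".

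**Step 1: reproduce the plan's figures.** 504 × 0.75 = 378, so 252 − 189 = 63 men are lost per arm. For power I used the Signorini Poisson-regression formula with null variance 4 and alternative variance 2 + 2/RR:

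z = [√(n × rate × (1 − R²)) × |ln RR| − 1.96 × √4] / √(2 + 2/RR)

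At 7% and RR 0.28: √(378 × 0.07 × 0.96) = 5.04; 5.04 × 1.273 − 3.92 = 2.50; 2.50 / √9.143 = 0.825; power 79.5%. The other three scenarios give 79.5%, 78.8% and 79.2%. The stated 80% is reproduced to within rounding of the ratios.

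**Step 2: expected events in the lowest scenario.** 189 × 0.07 = 13.2 and 189 × 0.02 = 3.8, so about 13 v 4. The other scenarios give 15.1 v 4.7, 17.0 v 5.7 and 18.9 v 6.8.

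**Step 3: add infections among the lost men.** With equal arm sizes the unadjusted Poisson likelihood-ratio statistic is 2[a ln(a/m) + b ln(b/m)], where m = (a + b)/2, on 1 degree of freedom.

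| Comparison v intervention events | Infections assumed among lost men (comparison, intervention) | Statistic | p |
|---|---|---|---|
| 13 v 4 | retained men only | 5.02 | 0.025 |
| 17 v 7 | 4, 3 | 4.30 | 0.038 |
| 17 v 8 | 4, 4 | 3.31 | 0.069 |

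Four infections in 63 is 6.3%, close to the 7% comparison rate. In expected values, with lost men at 7% in both arms, intervention incidence becomes (3.78 + 63 × 0.07)/252 = 3.25%, and the ratio moves from 2/7 = 0.29 to 3.25/7 = 0.46.

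For contrast, let lost men behave like retained men of their own arm (2% v 7%), which is what missing at random implies in this simple setting. Starting from the rounded 4 v 13, the ratio is then 0.30 with Poisson Wald p = 0.016. With lost men at 7% in both arms, the same calculation gives 0.48 and p = 0.08.

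**Step 4: how far to a change of direction.** With no infections among lost comparison men, one extra intervention infection (13 v 5) gives likelihood-ratio p = 0.055. Across the four scenarios, one or two such infections remove significance, depending on the test (Pearson, Fisher, Poisson Wald or exact conditional). The ratio reaches 1 at nine extra infections (13 v 13) and passes it at ten, or 10/63 = 16% of lost intervention men against none of the lost comparison men. If lost comparison men have four infections, passing 17 takes 18 − 4 = 14, or 14/63 = 22%.

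**Step 5: the opposite direction.** Suppose the full cohort had the planned effect: 252 × 0.07 = 17.6 and 252 × 0.02 = 5.0, so about 18 v 5, p = 0.005. If five comparison infections and no intervention infections fall among the lost, the retained data show 13 v 5, p = 0.055. Loss can mask an effect as well as weaken one.

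**Step 6: homelessness.** An arm's true rate differs from its retained rate by (fraction lost) × (lost rate − retained rate). The documents give no such difference. Assuming 10 to 20 points in one arm only, the shift is 0.25 × 10 = 2.5 to 0.25 × 20 = 5 points.

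**The case against.** **No positive result is at stake.** The plan reports a null STI finding. The 13 v 4 events and the 25% loss are planning inputs from the lowest of four scenarios at an intended 504, whereas Background gives 454 men. At 454 with 25% loss there would be about 170 per arm and 11.9 v 3.4 events. Observed events and loss by arm are not given. All of this stands. A reader might infer that a few infections among lost men would reverse the trial's result. The documents do not support that: there was no significant benefit to overturn, and Step 4 shows that even the hypothetical benefit changes direction only after ten or more extra infections in one arm.

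**The Poisson analysis is not unprotected.** A reader might infer that an analysis of retained men has no defence against attrition. It does have one: a correctly specified Poisson model is valid when loss depends only on arm and its four covariates, which include homelessness and employment. That is narrower than a longitudinal likelihood, but it is real.

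**Baseline values are already used in part.** In a difference-in-difference mixed model, baseline homelessness is already a response for the homelessness outcome, and likewise for employment. Adding it again as a covariate would put one value on both sides. This stands and limits the fix.

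**The drivers of loss are not documented, and retention was worked at.** The plan required two additional contacts, excluded men planning to leave the area, raised payments from $30 to $40 to $50, and discussed follow-up problems in supervision. These steps may reduce loss. They do not show that the remaining loss is unrelated to the outcome. Loss related to homelessness biases the arm contrast mainly where it differs by arm beyond what the observed data explain, and nothing in the documents settles whether it does.

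**Conclusion.** The point holds in a limited form. The plan credits its main model with a property that depends on missing at random, does not state that assumption, and plans no check of it. The assumption is open to doubt because the plan itself expects 25% loss and two outcomes are plausible causes of loss.

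On size: under the 7% v 2% planning scenario with 189 retained per arm, four infections among the lost men of each arm move p from 0.025 to 0.069 and the ratio from 0.29 to about 0.46. Nominal significance goes; direction does not. The reverse case, a real effect hidden by loss, is as easy to construct, so the null STI finding also needs the assumption made explicit.

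These figures rest on unadjusted two-arm counts. The p-values of the arm-by-time mixed model cannot be derived from the documents. The infections assigned to lost men and the 10 to 20 point homelessness difference are assumptions. The documents do not show that the reported conclusions are wrong, only that their robustness to loss is asserted and not examined.

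**What to change.** 1. Replace the sentence in the Analytic Plan with the actual assumption: outcomes are taken to be missing at random given arm, time, the covariates in the model and the outcomes observed. Report loss by arm at each follow-up, and by baseline homelessness, employment and STI status.
2. Keep baseline homelessness, employment and STI status in the models whatever the screening p-values, except where that baseline value is already a response in the same model.
3. Add a delta-adjusted multiple-imputation (tipping-point) analysis for incident STI and homelessness, with the shift varied separately by arm. State the range of shifts as an assumption, report the shift at which the conclusion changes in either direction, and label the analysis as added after the results were known.

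All three use data already collected. The cost is a little more analysis work and less favourable wording on robustness.

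### Covariates enter the primary models by p-value screens; for incident STI the outcome screen would drop a risk-doubling non-demographic covariate more often than not at the planned event count, with no check of arm balance

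*Combined protocol and SAP*

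**What the plan says.** The Analytic Plan section states two rules for the primary mixed-effects models. The first is "Demographic covariates were included in all outcome models if they were significantly associated with treatment group at baseline in bivariate chi-squared tests", at p<0.20. The second is "For each outcome, additional potential covariates were included if they were associated with the given outcome in bivariate chi-squared tests", at p<0.05. The first rule looks at arm and is tied to baseline. The second looks only at the outcome and names no visit. There is no list of candidate covariates, and none is forced into the model. The treatment effect is the time-by-arm interaction.

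The Power Calculation section works differently. It assumes a Poisson model "adjusting for age, marital status, employment and homelessness", and it reports that an analysis on those lines was also run and was null for incident STI.

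The Background section describes the design: "The two armed quasi-experimental evaluation study enrolled participants in either the MEN Count counseling intervention or an attention comparison group". The Pilot Testing section refers to an RCT, but no allocation method is described anywhere.

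**The concern.** In a study called quasi-experimental, covariate adjustment is a main defence against differences between the arms. The variables most likely to confound an STI comparison are behavioural: number of partners, condom use, transactional sex, substance use. Under the stated rules these are never compared between arms. One that is clearly unbalanced stays out of the model unless its own association with the outcome reaches p<0.05.

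For a rare outcome that test has little power, so chance largely decides which confounders are removed, and the same outcome data are used both to choose the model and to estimate the effect. What is at stake is bias in the estimated STI effect, in whichever direction the imbalance runs.

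Because no visit is given for the outcome screen, the wording also does not prevent a value measured after allocation from being admitted. The Background section lists masculinity ideologies and social-cognitive factors as expected mediators, and employment and homelessness as outcomes. Adjusting for later values of these could remove part of the effect under study.

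**Working it through.** **Inputs from the Power Calculation section.** The calculation is "based on an intended sample size of 504 and assumed two-sided tests with a 0.05 type I error rate". With 25% attrition, 504 × 0.75 = 378 men, "with proportion of 0.50 (i.e. 189 participants) in each group". Comparison-group incidence is 7, 8, 9 or 10%; intervention incidence is 2, 2.5, 3 or 3.6%; rate ratios are 0.28, 0.31, 0.34 and 0.36; R-squared is 0.04.

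**Step 1: reproduce the stated power.** For Poisson regression on a binary variable (Signorini's method), z = [√(N(1−R²)λ₀)·|ln RR| − 1.96√V₀] / √V₁, with V₀ = 1/(0.5×0.5) = 4 and V₁ = 1/0.5 + 1/(0.5·RR). For 7% and RR 0.28: N(1−R²)λ₀ = 378 × 0.96 × 0.07 = 25.4, so z = (5.04 × 1.273 − 3.92)/√9.14 = 0.825 and power is 0.795. The four scenarios give 0.795, 0.795, 0.788 and 0.792 (0.80-0.81 with R² = 0). The stated 80% is reproduced to rounding.

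**Step 2: implied infections.**
- Target effect: 189 × (0.07 + 0.02) = 17.0, up to 189 × (0.10 + 0.036) = 25.7.
- Equal arms: 378 × 0.07 = 26.5, up to 378 × 0.10 = 37.8.

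The documents give no observed count.

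**Step 3: power of the outcome screen.** Take a binary covariate with prevalence q (not in the documents, so assumed) and risk ratio 2. Risks are r/(1+q) without it and 2r/(1+q) with it, where r is overall risk. The 5% chi-squared threshold is 3.84. By hand for q = 0.3, using z = difference / √[r(1−r)(1/113.4 + 1/264.6)]:

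| Infections | r | Risks | z | Chi-squared |
|---|---|---|---|---|
| 17.0 | 0.045 | 3.5% v 6.9% | 1.49 | 2.2 |
| 25.7 | 0.068 | 5.2% v 10.5% | 1.85 | 3.4 |
| 37.8 | 0.100 | 7.7% v 15.4% | 2.28 | 5.2 |

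In the first two rows the expected result falls short of the threshold. Simulated probabilities of retention (200,000 runs, no continuity correction):

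| Infections | q = 0.1 | 0.2 | 0.3 | 0.4 | 0.5 |
|---|---|---|---|---|---|
| 17.0 | 0.25 | 0.31 | 0.33 | 0.32 | 0.29 |
| 25.7 | 0.33 | 0.42 | 0.46 | 0.45 | 0.42 |
| 37.8 | 0.43 | 0.56 | 0.61 | 0.62 | 0.59 |

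Continuity correction, or prevalence of 60-80%, lowers these. About 29-33 infections are needed for 50% retention and 57-64 for 80% (prevalence 20-50%).

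**Step 4: effect on the STI estimate if the contrast is follow-up only.** For scale, one omitted covariate with risk ratio 2 and a 10-point imbalance shifts a crude rate ratio by 1.55/1.45 = 1.07 or 1.35/1.25 = 1.08, that is 7-8%. With several covariates (assumed: 378 men, 8% risk, no true effect, three or four covariates with odds ratio 2, each unbalanced by 8-15 points in the intervention arm's favour):
- Screened model: median odds ratio 0.89-0.93, false positives 5.4-6.9%.
- Fixed set: median odds ratio 0.98-1.02, false positives 5.1-5.8%.

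A repeat with 4,000 runs per cell at prevalence 0.4 gave 0.87-0.95 against 1.00, and false positives of 4.9-6.4% against 4.6-5.9%. These runs have 378 × 0.08 = about 30 infections, where 45-48% of the covariates were retained.

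**Step 5: the same imbalance under a time-by-arm contrast.** Take STI as 13% at baseline (the pilot figure) and 8% at follow-up, with every one of these covariates omitted. The follow-up-only odds ratio is 0.64-0.85, but the ratio of follow-up to baseline odds ratios is 0.99-1.00.

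**The case against.** The strongest reply is that the plan's effect is a time-by-arm interaction, not a follow-up contrast. Step 5 shows that a stable imbalance then cancels almost completely. This stands wherever the model contains a baseline value of the outcome, as it can for sexual risk, homelessness and unemployment. For incident STI it is unsettled, because the documents do not say how an incident outcome is coded at baseline. If it has no baseline value, covariates act directly on the arm contrast.

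The second reply is that a fixed-covariate STI analysis was run and was null. That answers part of the point. But it is supplementary, covers only incident STI, and its four covariates include no sexual-behaviour or substance-use variable.

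Several stronger readings are tempting and are not supported:
- **That most confounders were in fact left out.** The 17-26 range assumes a 64-72% reduction. With equal arms there would be 26-38 infections, and at 38 about half or more are kept at most prevalences. If the screen used baseline STI (454 × 0.13 = about 59 cases), retention would be 0.58-0.81.
- **That this applies to demographic confounders.** An unbalanced one can enter through the p<0.20 arm screen whatever its link to STI.
- **That the arm screen contradicts the assumed R-squared of 0.04.** With 378 men, p<0.20 needs an R-squared of only 1.64/378 = 0.004.
- **That false positives are materially inflated.** The ranges overlap, and simulation error at 1,500 runs is about 0.6 points.
- **That mediators were adjusted for.** The text is silent on timing and treats mediation as a separate question. This is a gap in wording, not evidence that it happened.

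**Conclusion.** The concern holds in limited form. The primary models choose covariates by significance, and non-demographic ones have no arm-balance check and no stated visit. At the planned 17-26 infections, a non-demographic covariate that doubles STI risk is kept about 25-46% of the time. This rests on assumed prevalence of 10-50% and on screening against follow-up STI.

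The consequence is moderate bias, not a false-positive problem: an odds ratio of about 0.89-0.93 where the truth is 1.0. It requires a follow-up-only contrast and three or four covariates unbalanced in the same direction. The reverse imbalance would push the estimate above 1. The shift is small beside the target ratios of 0.28-0.36, and it nearly disappears if a baseline STI value is in the model. The documents do not show that the reported null STI result is wrong. They show that its adjustment cannot be judged from the stated rules.

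**What to change.** Replace both screening rules with one fixed set of baseline-only covariates: age, marital status, employment, homelessness and baseline sexual-risk level. Three conditions apply:
- In each repeated-measures model, omit the baseline value of that model's own outcome, because it is already a response. This means leaving out sexual-risk level, homelessness or employment in turn.
- Adjust for no value measured after allocation.
- For incident STI, the set may be entered as a single propensity score for arm, so that it costs one parameter against few events.

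The text should also say how incident STI is coded at baseline, at which visit the existing outcome screen was applied, and which covariates each screen admitted. The Outcome Definitions section leaves some men out of the sexual-risk analysis, so their coding on that covariate needs stating.

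Because analyses have already been run, the screening sentences should stay as a record of what was done. Report the fixed-set models beside the screened results as a labelled re-analysis. The cost is wording, one re-run and a slight loss of precision if some fixed covariates prove unhelpful. Merely loosening the outcome screen to p<0.20 would be weaker: retention would be only 0.45-0.58 at 17 infections and 0.54-0.71 at 25.7.
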